**5.3.4                   *Visit 3, Week 4, Day 22***

- Concomitant and Prior Medications
- Vital Signs
- Hematology
- Chemistry
- IL-6
- hs-CRP
- Ziltivekimab trough PK
- ADA (pre-dose)
- Coagulation (INR): Patients on warfarin only
- Adverse Events
- CARES Corvidia ePRO
- PGIS

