#### **5.3.7                   *Visits 6 through 9, Weeks 9 through 21***

- Concomitant and Prior Medications (not Week 12)
- Vital Signs (not Week 12)
- BMI (Week 13 only)

- Hematology (not Week 12)
- Lipids (fasting 8 hours; Week 13 only)
- Chemistry (not Week 12)
- Spot urine protein-creatinine ratio (Week 13 only)
- Urinalysis (including albumin) (Week 13 only)
- Iron Indices (Week 13 only)
- Serum hepcidin (Week 13 only)
- Special RBCs (Week 13 only)
- IL-6 (pre-dose) (not Week 12)
- hs-CRP (not Week 12)
- Ziltivekimab trough PK (not Week 12)
- ADA (pre-dose) (not Week 12)
- CKD Biomarkers (Week 13 only)
- NT-pro-BNP (Week 13 only)
- Lp(a), ApoB, ApoA1 (fasting 8 hours; Weeks 9 and 13 only)
- Lipid profile by NMR spectroscopy (fasting 8 hours; Week 13 only)
- Cardiac Risk Biomarkers: SSA, fibrinogen and ST2 (Week 13 only)
- Storage samples for Exploratory Biomarkers and RNA Testing (Week 13 only)
- Coagulation (INR): Patients on warfarin only (not Week 12)
- Adverse Events (not Week 12)
- PROMIS® 13a and Fatigue Items (Week 13 only)
- PROMIS® Sexual Interest Items (Week 13 only)
- CARES Corvidia ePRO (Week 12 only)
- PGIS (Week 12 only)
- PGIC (Week 13 only)
- EQ-5D-5L (Week 13 only)
- Optum SF-36 v2 (Week 13 only)

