**5.3.9                   Visit 10, Week 23 and Visit 11, Week 24/ET**

- Concomitant and Prior Medications
- Vital Signs
- BMI (Week 24 only)
- Hematology
- Lipids (fasting 8 hours)
- Chemistry
- Urinalysis (including albumin); portion stored frozen at Week 24 only
- Iron Indices
- Serum hepcidin (Week 24 only)
- Special RBCs (Week 24 only)
- IL-6
- hs-CRP
- Ziltivekimab trough PK
- ADA
- 12-lead ECG (Week 24 only)
- CKD Biomarkers
- NT-pro-BNP
- Lp(a), ApoB, ApoA1 (fasting 8 hours)
- Lipid profile by NMR spectroscopy (fasting 8 hours)
- Cardiac Biomarker: SSA, fibrinogen and ST2 (Week 24 only)
- Storage samples for Exploratory Biomarkers and RNA Testing (Week 24 only)
- Limited Physical Examination (Week 24 only)

- Coagulation (INR): Patients on warfarin only
- Adverse Events
- PROMIS® 13a and Fatigue Items
- PROMIS® Sexual Interest Items (Week 24 only)
- CARES (Corvidia ePRO) [2 weeks after Week 21 (Dose 6) for 14 consecutive days]
- PGIS (Week 24 only)
- PGIC (Week 24 only)
- Optum SF-36 v2®
- EQ-5D-5L (Week 24 only)

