#### ***11.4.3 Efficacy Analysis***

For all efficacy variables, the number of patients (n), mean, standard deviation (SD), median, quartiles (Q1 and Q3), minimum (min) and maximum (max) values for the observed value, change from baseline, or percent change from baseline (as applicable) will be reported. The difference (Ziltivekimab - Placebo) in changes or percent changes (as applicable) will be presented.

A mixed model for repeated measures (MMRM) will be used to evaluate change or percent change from baseline. The model will include variables for baseline hemoglobin ( $\geq 11$  or  $< 11$  g/dL), CKD Stage (3, 4 or 5), treatment group, visit and treatment group-by-visit interaction as categorical fixed effects, baseline value and baseline-by-visit interaction will be included as covariates. The least squares means for each dose, the least squares mean differences from placebo along with the associated 95% confidence intervals (CIs) and p-values will be presented. If the normality assumption is not met, a nonparametric test will be selected for efficacy analysis. Details of normality test and nonparametric test will be provided in the Statistical Analysis Plan.

An unstructured covariance matrix will be used to model the within-subject correlation. The Kenward-Roger approximation will be used to adjust the denominator degrees of freedom. The analysis will be performed based on all observed post-baseline scores without any imputation of missing data. In the case when the MMRM fails to converge using an unstructured covariance matrix in any stage, a less stringent covariance matrix (e.g., autoregressive 1) will be used.

Sensitivity analyses will be conducted to explore the robustness of the result for primary efficacy endpoint based on MMRM. Full details will be pre-specified in SAP and documented prior to database lock of the study.

The differences in proportions and 95% CIs will be based on the normal approximation to binomials.

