#### 11.4.4.1 Primary

- Difference in percent change in hs-CRP levels from Baseline (average of the hs-CRP value prior to randomization and Day 1) to Week 13 between each active group and placebo.

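### The fallback covariance is described as 'less stringent', but its only example, AR(1), is more restrictive than unstructured and forces one variance on all visits, so Week 13 intervals can be too narrow or too wide if it is used

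*Protocol*

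**What the plan says.** Section 11.4.3 sets the primary covariance: "An unstructured covariance matrix will be used to model the within-subject correlation". It then fixes the inference: "The Kenward-Roger approximation will be used to adjust the denominator degrees of freedom". The fallback is triggered as follows: "In the case when the MMRM fails to converge using an unstructured covariance matrix in any stage". In that event "a less stringent covariance matrix (e.g., autoregressive 1) will be used". No other structure is named, and no robust variance is mentioned.

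The primary comparison in section 11.4.4.1 is the percent change in hs-CRP from baseline "to Week 13 between each active group and placebo".

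The hs-CRP visits come from section 5.3. They are Week 4 ("Visit 3, Week 4, Day 22"), Week 5 (section 5.3.5), Weeks 9, 13, 17 and 21 (section 5.3.7, "hs-CRP (not Week 12"), and Weeks 23 and 24 ("Visit 10, Week 23 and Visit 11, Week 24/ET"). Section 5.4 adds hs-CRP at Weeks 28 and 32 in the safety follow-up.

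**The concern.** A fallback is used when the full covariance cannot be estimated. It must then have fewer parameters, which means more constraints. AR(1) is among the most constrained choices: one variance for every visit, and one correlation parameter raised to the number of visits between two measurements. It is less demanding only for the fitting algorithm.

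The equal-variance constraint is the one that matters. Under AR(1) the standard error at Week 13 is built from an SD pooled over all visits. If the true Week 13 SD is larger than that, the interval is too short and the test rejects too often; if it is smaller, the reverse holds. Kenward-Roger allows for the small-sample uncertainty in estimating the assumed covariance. It does not correct a wrong structure.

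There is some reason to doubt a common variance. Percent change cannot go below -100% but has no upper bound. Some hs-CRP samples are taken pre-dose at the end of a cycle and others two to three weeks after a dose. The half-life of 48 to 56 days in CKD patients (section 3.5.4.1) implies accumulation. None of this shows which way Week 13 would differ.

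What is at stake is mainly the precision reported for each dose against placebo. The trial exists to choose a dose for an outcome trial (section 2), and section 11.4.3 applies the same model to endpoints with smaller expected effects.

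**Working it through.** **Reproducing the plan's own figure.** Section 11.1 gives a difference of -60.74 points, an SD of 16.893 (Week 4 of an earlier study), 54 evaluable per group, and two-sided alpha 0.05. The noncentrality is 60.74 / (16.893 × √(2/54)) = 18.7, so power is essentially 100%, as stated. With 10% dropout, 54 / 0.9 = 60 per group, also as stated.

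**Parameter count.** Unstructured with K visits has K(K+1)/2 parameters: 36 for eight visits, 10 if the model ends at Week 13 (Weeks 4, 5, 9, 13), and 55 if Weeks 28 and 32 are included. AR(1) always has 2.

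**Effect on the Week 13 interval.** With complete data and a treatment-by-visit model, AR(1) uses the pooled SD, s_pool = √(mean of s_k²). The ratio of reported to true standard error is about s_pool / s_13, and type I error is 2 × [1 − Φ(1.96 × ratio)]. The SD patterns below are assumptions; trends are linear in weeks.

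| Assumed SD pattern | s_pool | s_13 | SE ratio | Type I error |
|---|---|---|---|---|
| Equal at all 8 visits | 1 | 1 | 1.00 | 5.0% |
| Week 13 alone +25%, 8 visits | √((7 + 1.5625)/8) = 1.035 | 1.25 | 0.83 | 10.5% |
| Week 13 alone +50%, 8 visits | √((7 + 2.25)/8) = 1.075 | 1.5 | 0.72 | 16.0% |
| Week 13 alone −25%, 8 visits | √((7 + 0.5625)/8) = 0.972 | 0.75 | 1.30 | 1.1% |
| Rising 1 to 1.5, Weeks 4 to 24 | 1.276 | 1.225 | 1.04 | 4.1% |
| Falling 1.5 to 1, Weeks 4 to 24 | 1.251 | 1.275 | 0.98 | 5.4% |
| Rising 1 to 1.25, Weeks 4 to 13 (4 visits) | 1.109 | 1.25 | 0.89 | 8.2% |
| Rising 1 to 1.5, Weeks 4 to 13 (4 visits) | 1.224 | 1.5 | 0.82 | 11.0% |

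**Check by simulation.** Four arms of 60, eight visits, about 10% dropout, AR(1) fitted by REML on visit order, 1,500 runs per scenario (Monte Carlo error about 0.6 points at 95%). Coverage of the nominal 95% interval at Week 13:

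- SD +25%: 91.0%.
- SD +50%: 83.2% when the true correlation is the same for all pairs of visits, 80.7% when it decays with weeks.
- SD −25%: 99.3%.
- Equal SDs, with only the correlation shape or spacing wrong: 95.2% to 95.6%.

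When the Week 13 SD was estimated from Week 13 data, coverage was 94% to 96% across the scenarios. The loss therefore comes from the equal-variance constraint. The visit gaps (1, 4, 4, 4, 4, 2 and 1 weeks) are not what does the damage.

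**Effect on the planned test.** If the standard error were 1.30 times too large, the expected test statistic would still be about 18.7 / 1.30 = 14.4. At 54 per group the SD could reach about 73.6 before power fell to 99%.

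**The case against.** The case on the other side is substantial.

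- *AR(1) is only an example, and section 11 sends details to the SAP.* This stands in part. The absence of an ordered list from the protocol is no fault, and a reader might infer that the protocol commits the trial to AR(1), which it does not. But the one example it gives is a poor one and its description is wrong. Both are in the protocol's own text.
- *The fallback may never be used.* This stands. It needs non-convergence, and nothing in the document makes that likely with 240 patients and 10% dropout. A model ending at Week 13, which the 13-week primary analysis in section 12.2 would permit, has only 10 covariance parameters. Section 11.4.3 also provides a nonparametric test if normality fails, which could displace the MMRM altogether.
- *The largest error rates come from one unfavourable pattern.* This stands. Week 13 is a pre-dose visit like Weeks 5, 9, 17 and 21, and the protocol offers no reason for its SD alone to be raised. With eight visits Week 13 lies mid-series, so a smooth trend nearly cancels. It does not cancel if the model stops at Week 13.
- *Unequal spacing.* A reader might infer that treating gaps of 1, 2 and 4 weeks alike also distorts the Week 13 interval. The mismatch is real, but on its own it leaves coverage at about 95%.
- *The dose-sequence tests are safe.* A reader might infer that the primary conclusion is in doubt. At the effect in section 11.1, a standard error wrong by 20% to 30% would not change a rejection.

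**Conclusion.** The point holds in a limited form and is best treated as a cheap improvement. AR(1) is more restrictive than unstructured, and its equal-variance assumption makes model-based Week 13 intervals and p-values wrong when the Week 13 variance is not close to the average over visits. The error can go either way. Under the assumed patterns type I error runs from about 1% to 16%, and it stays near 5% if the SD is constant or drifts smoothly over eight visits. The protocol has no data that would choose between these patterns.

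The conclusion depends on three conditions: the unstructured fit fails, AR(1) is then chosen, and model-based standard errors are kept. What is exposed is the validity of the intervals used to compare doses and of tests on endpoints with smaller effects.

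**What to change.** In section 11.4.3, delete 'less stringent' and the AR(1) example. State in the protocol or SAP, before unblinding, an ordered fallback that keeps a separate variance for each visit: for example heterogeneous Toeplitz, then heterogeneous AR(1) or heterogeneous compound symmetry. The exact order is a matter of judgement; visit-specific variances are the essential part. For any structure other than unstructured, use empirical (sandwich) standard errors with degrees of freedom suited to them, for example between-within, in place of Kenward-Roger.

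The cost is one sentence and a few lines of code. When the fallback is used, the interval may be slightly wider. The change also removes a choice that would otherwise be made after seeing the data.

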## **2 STUDY GOAL AND OBJECTIVES**

Patients with NDD-CKD, who have evidence of systemic inflammation with increased cardiovascular risk, will be enrolled into this trial. The purpose of this trial is to determine a dose to select for a potential cardiovascular outcome trial with Ziltivekimab. The current trial will determine which dose of Ziltivekimab will have a significant reduction in hs-CRP with acceptable increases in LDL-C or triglycerides and without clinically meaningful reductions in neutrophils and platelet counts. Doses to be tested will be 7.5 mg, 15 mg and 30 mg subcutaneous monthly compared to placebo for six months.

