### **3.5.4            *Rationale for the Dose Regimens***

The main goal of Ziltivekimab dosing in the planned Phase 1/2 CKD patient study is to attain and maintain serum Ziltivekimab concentrations sufficient for  $\geq 90\%$  IL-6 binding over the treatment period, with a secondary goal of reducing hs-CRP to below 2 mg/L while keeping the highest planned dose more than 20-fold below the no adverse effect level (NOAEL) observed in primates.

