### 11.2 Randomization

Approximately 240 patients will be randomized 1:1:1:1 to Ziltivekimab Dose #1 (7.5 mg), Ziltivekimab Dose #2 (15 mg) or Ziltivekimab Dose #3 (30 mg) or Placebo as they became eligible to proceed with dosing on Day 1. Patient randomization will be stratified by baseline hemoglobin ( $\geq 11$  or  $< 11$  g/dL) and CKD stage (3, 4 or 5). Approximately 240 patients will be randomized 1:1:1:1 (60 per group) into the trial.

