#### 11.4.4.3 Exploratory

- Difference in percent change in hs-CRP levels from Baseline to End of Treatment (Weeks 23 through 24) between each active group and placebo.
- Difference in percent change in serum NT-pro-BNP from Baseline (average of the NT-pro-BNP value prior to randomization and Day 1) to Week 13 and to End of Treatment (Weeks 23 through 24) between each active group and placebo.
- Difference in change in SAA from Baseline to End of Treatment (Weeks 23 through 24) between each active group and placebo.
- Difference in percent change in fibrinogen from Baseline to End of Treatment (Week 24) between each active group and placebo.
- Difference in change in hemoglobin from Baseline (average of the two most recent hemoglobin values prior to randomization and Day 1) to Week 13 and to End of Treatment (Weeks 23 through 24) between each active group and placebo.
- Difference in change in serum albumin from Baseline (average of the two most recent serum albumin values prior to randomization and Day 1) to Week 13 and to End of Treatment (Weeks 23 through 24) between each active group and placebo.
- Proportion of patients achieving hs-CRP response at Week 13 and to End of Treatment (Weeks 23 through 24), defined as hs-CRP <2.0 mg/L in each active group and placebo.
- Difference in change in ST2 from Baseline to Week 13 and to End of Treatment (Week 24) between each active group and placebo.
- Difference in percent change in Lp(a) from Baseline to Week 13 and to End of Treatment (Weeks 23 through 24) between each active group and placebo.

- Difference in percent change in LDL-C, triglycerides, ApoB, ApoA1, ApoB/ApoA1, and lipid profile by NMR spectroscopy from Baseline to Week 13 and to End of Treatment (Weeks 23 through 24) between each active group and placebo.
- Difference in change of creatinine based eGFR and cystatin C-based eGFR from Baseline to Week 13 and to the End of Treatment (Weeks 23 through 24) between each active group and placebo.
- Difference in change of UACR from Baseline to Week 13 and to End of Treatment (Weeks 23 through 24) between each active group and placebo.
- Difference in change of the total fatigue score (PROMIS Fatigue 13a short form and selected items from the PROMIS Fatigue item bank) from Baseline to Week 13 and to End of Treatment (Weeks 23 through 24) between each active group and placebo.

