#### **11.4.7 *Exploratory Analyses of Efficacy and Safety Endpoints Based on Baseline Hemoglobin ( $\geq 11$ or $< 11$ g/dL).***

Exploratory analyses may be performed for the primary and secondary efficacy endpoints with a stratified analysis by baseline hemoglobin ( $\geq 11$  or  $< 11$  g/dL) and CKD stage (3, 4 or 5).

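### The exploratory hs-CRP <2.0 mg/L response is compared without adjusting for baseline hs-CRP or the randomization factors: an avoidable loss of precision, not a bias

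*Protocol*

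**What the plan says.** Section 11.4.3 of the protocol sets two kinds of comparison. Change and percent-change endpoints go into a mixed model for repeated measures with hemoglobin stratum, CKD stage, treatment, visit and treatment-by-visit, and "baseline value and baseline-by-visit interaction will be included as covariates". Proportions get one sentence: "The differences in proportions and 95% CIs will be based on the normal approximation to binomials". It names no covariate and no stratum.

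The endpoint governed by that sentence is in section 11.4.4.3: "Proportion of patients achieving hs-CRP response at Week 13 and to End of Treatment (Weeks 23 through 24), defined as hs-CRP <2.0 mg/L". It is exploratory and lies outside the sequential test in section 11.4.4.4.

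Three other places bear on it:

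- Section 3.5.4 explains the dose regimens by a main goal of at least 90% IL-6 binding, "with a secondary goal of reducing hs-CRP to below 2 mg/L".
- Section 11.2 states: "Patient randomization will be stratified by baseline hemoglobin". CKD stage is the other factor.
- Section 11.4.7 states: "Exploratory analyses may be performed for the primary and secondary efficacy endpoints with a stratified analysis". These analyses are optional, and the exploratory responder endpoint is not among the endpoints covered.

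**The concern.** Response is a fixed cut on the same marker that was measured at entry, so it depends mechanically on the starting value. A patient at 2.2 mg/L reaches 2.0 with a fall of (2.2 - 2.0)/2.2 = 9%. A patient at 20 mg/L needs (20 - 2.0)/20 = 90%. Chance differences in baseline hs-CRP between arms of 54 to 60 patients therefore add noise to the raw response rates. The protocol removes that noise for change endpoints but leaves it in here.

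At stake is the width of the confidence intervals on an endpoint that readers will set side by side across three doses. Its threshold is the one used in the canakinumab threshold analysis described in section 1.1.1.3.

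**Working it through.** **1. The plan's own figures.** Section 11.1 gives a difference of 60.74 points, SD 16.893 and 54 per group. The noncentrality is (60.74/16.893) × sqrt(54/2) = 3.596 × 5.196 = 18.7, so power is effectively 1, in agreement with the stated value above 99%. Dropout: 54/0.90 = 60. Both figures reproduce. They concern the primary endpoint; the protocol states no response rate, power or sample size for the responder endpoint.

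**2. Precision of the raw difference.** Half-width = 1.96 × sqrt[p0(1 - p0)/n + p1(1 - p1)/n]. With n = 54 and assumed rates p0 = 0.091 and p1 = 0.404, this is 1.96 × sqrt(0.001532 + 0.004459) = 1.96 × 0.0774 = 0.152, or about 15 points. Over assumed placebo rates of 5-20% and active rates of 30-85%, it runs from about 11 to 17 points.

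**3. What baseline adjustment gains.** All inputs in this step are assumptions except n = 54 and the 61% reduction, which borrows the 60.74 in section 11.1. Baseline hs-CRP is lognormal with median 5.5 mg/L and log SD 0.8, truncated at 2.0 or above. Placebo has no mean change on the log scale and log SD 0.6. Active arms have a reduction of 61%, 75% or 90% and log SD 0.4, 0.7 or 1.0. Each scenario has 1,000 simulated trials of 54 against 54. The adjusted estimate comes from a logistic model of response on treatment and ln baseline: the mean over all patients of the predicted risk under active minus the predicted risk under placebo. The variance cut is 1 - (SE adjusted / SE raw)².

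| Reduction, active log SD | Raw difference | Adjusted difference | SE raw | SE adjusted | Variance cut | Half-width, raw to adjusted (points) |
|---|---|---|---|---|---|---|
| 61%, 0.4 | 0.313 | 0.313 | 0.0773 | 0.0634 | 32.6% | 15.1 to 12.4 |
| 61%, 0.7 | 0.322 | 0.322 | 0.0773 | 0.0693 | 19.7% | 15.1 to 13.6 |
| 61%, 1.0 | 0.333 | 0.333 | 0.0777 | 0.0713 | 15.8% | 15.2 to 14.0 |
| 75%, 0.4 | 0.528 | 0.530 | 0.0797 | 0.0653 | 32.9% | 15.6 to 12.8 |
| 75%, 0.7 | 0.498 | 0.499 | 0.0811 | 0.0711 | 23.1% | 15.9 to 13.9 |
| 75%, 1.0 | 0.484 | 0.483 | 0.0798 | 0.0729 | 16.5% | 15.6 to 14.3 |
| 90%, 0.4 | 0.825 | 0.825 | 0.0536 | 0.0486 | 17.9% | 10.5 to 9.5 |
| 90%, 0.7 | 0.781 | 0.780 | 0.0594 | 0.0541 | 17.0% | 11.6 to 10.6 |
| 90%, 1.0 | 0.731 | 0.731 | 0.0639 | 0.0594 | 13.8% | 12.5 to 11.6 |

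The two estimates agree within 0.002. The half-width narrows by 0.9 to 2.8 points.

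**4. Sensitivity to the assumptions.** A different set (median 6 mg/L, between/within log SD 0.8/0.5 or 1.0/0.6, selection on a screening value of at least 2.0) gave variance cuts of 14-18% for reductions of 50-80%. Under the same distributions, taking baseline as section 11.4.4.1 defines it (the average of the value before randomization and Day 1), the cut was about 18-28% and the half-width narrowed by about 1.3 to 2.3 points.

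The randomization strata were not simulated, so no gain is claimed for them.

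**The case against.** **The endpoint is minor.** It is exploratory, has no power claim and is promised only a difference with an interval. This stands, and it sets the severity.

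**The dose decision rests elsewhere.** A reader might infer that the trial's dosing goal is judged on this comparison. The documents do not support that. Section 3.5.4 calls the threshold a secondary goal, in a paragraph on the choice of regimens. Section 2 puts the decision on hs-CRP reduction, "The current trial will determine which dose of Ziltivekimab will have a significant reduction in hs-CRP", weighed against lipids, neutrophils and platelets. The hs-CRP reduction is analysed in the model that does adjust for baseline.

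**Nothing is biased.** A reader might also infer that the raw difference is invalid, or that patients already below 2.0 on Day 1 distort it (7-9% of patients under the assumptions of step 4). Randomization places such patients in every arm, and the raw and adjusted estimates coincide.

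**Large contrasts will not change.** With assumed rates of 10% against 50% or more, unadjusted power at 54 per arm is already at least 99.8%. It is 75% for 10% against 30% and 22% for 20% against 30%, so precision matters only for smaller contrasts.

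**Adjustment does not settle the dose order.** Under the distributions of step 4, with assumed reductions of 50/65/80%, the observed response rates misordered the active arms in 4-8% of trials raw and 2-5% adjusted. With 70/75/80% the figures were 29-35% and 23-31%. Adjustment helps, but a fragile order stays fragile at this arm size.

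**It could be left to the SAP.** Section 11 leaves details to the SAP, and an adjusted estimate there would contradict nothing. That is true, but section 11.4.3 defers the normality test, the nonparametric test and the sensitivity analyses by name. For proportions it fixes the binomial method itself.

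**Conclusion.** The point holds as a matter of efficiency. The protocol fixes an unadjusted comparison for the one response endpoint, although response is mechanically tied to its baseline value and the protocol adjusts its change endpoints. The cost is a risk-difference variance roughly 14-33% larger than it could be made, or about 1 to 3 percentage points of 95% half-width at 54 per arm.

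These figures rest on assumed lognormal distributions and assumed reductions. The direction was the same in every scenario, but the size would move with the real data. Severity is minor: an optional precision improvement, with no effect on the validity of the planned estimate.

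**What to change.** Replace the sentence on proportions in section 11.4.3. Estimate the responder risk difference for each dose against placebo by logistic regression with treatment, ln(baseline hs-CRP, as defined in section 11.4.4.1) and the randomization strata. Standardise it over all patients and give a delta-method or bootstrap 95% CI. Keep the raw proportions per arm as description.

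Before that, reconcile the coding of CKD stage. Section 3.3.1 names stages 3, 4 or 5 and then says that stratification uses two categories, stage 3 and stages 4 or 5. Sections 11.2 and 11.4.3 give only the three-stage form. The model should carry the factor as it was used in randomization.

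The cost is a few lines of text and code. Baseline hs-CRP and the strata are already collected, and no patient, visit or sample is added.
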